A randomized controlled study compares lung ultrasonography to fiberoptic bronchoscopy confirming double lumen tube positioning for thoracic surgery

Study Protocol

NCT03314519

Version Mar, 10th 2020

[name]^a,

^aDepartment of Anesthesiology, Faculty of Medicine Siriraj hospital, Mahidol university, Bangkok, Thailand

[name]^a,

^aDepartment of Anesthesiology, Faculty of Medicine Siriraj hospital, Mahidol university, Bangkok, Thailand

[name]^a,

^aDepartment of Anesthesiology, Faculty of Medicine Siriraj hospital, Mahidol university, Bangkok, Thailand

[name]^b,

^bDepartment of Surgery, Faculty of Medicine Siriraj hospital, Mahidol University, Bangkok, Thailand

[name]^a

^aDepartment of Anesthesiology, Faculty of Medicine Siriraj hospital, Mahidol university, Bangkok, Thailand

Study Protocol

Background

Double-lumen endobronchial tubes is one of well-known technique for one-lung ventilation due to simplicity and high success rate of lung separation compare with bronchial blocker(1). The Blind technique is a current popular method for lung separation compare with the fiberoptic-guided method due to simplicity and a shorter period time to apply(2). Because blind intubation for double lumen tube is still more popular, evaluation for tube position is an essential part of the practice. The sensitivity of clinical guided for good lung collapse was 84.5% and specificity 41.1%(3) and even lower in an older study(4, 5), which was unreliable and vary due to subjective skills. Recently, evidence nowadays recommended the use of clinical and fiberoptic-guided check for the proper position(6).

Currently, fiberoptic bronchoscopy for evaluation for the position of DLT was considered as the gold standard. Not only evaluation for positioning, but also an adjustment for tube position(7). Though, proper tube positioning is not equal lung collapse. And in some patients with abnormal anatomy or secretion or bleeding in the airway, fiberoptic bronchoscopy is difficult or even impossible.

Instead, lung ultrasonography is a novel, safe and easy way to detect lung collapse, which has high sensitivity and specificity(5). There is also a study report 88% of accuracy of lung ultrasound in the diagnosis of anesthesia-induced atelectasis in children(8,9). The recent study also reports superior lung ultrasonography over clinical methods. Meanwhile, the misplacement of DLT in both groups could not be ensured(3). Therefore, this method might be useful for caring for thoracic patients. However, due to its new method, lung ultrasonography needs some practice and learning curve(10).

Objectives: This study aimed to demonstrate that using lung ultrasonography to confirm lung collapse resulted from proper positioning of the double lumen tube (DLT) is a comparable method to using fiberoptic bronchoscopy to confirm the DLT position.

Design: a non-inferiority randomized controlled study

Setting: A tertiary care university hospital, single institution

Participants: Two-hundreds patients with ASA classification 1-3 scheduled for elective thoracic surgery who require a left-side double lumen tube were enrolled and randomized into 2 groups. Five patients were dropped out from the protocol deviation.

Interventions:

In group FOB (n=98), standard fiberoptic bronchoscope was used to confirm the position of the DLT and adjusted the tube to proper position, while in group US (n=97), lung ultrasound was scanned in 4 zones including upper and lower lobe at flank and back of patient at the side of surgery to confirm the lung collapse resulted from proper positioning of the DLT and used to aid repositioning of the DLT if required.

Outcome Measurements: The degree of lung collapse was determined by visual grading by surgeon. Time used to adjust the DLT position was recorded.

Statistical Analysis

Sample size calculation was performed by *Mario de Bellis et al* (11) report that fiberoptic bronchoscopy provided a sensitivity of 95% for optimal LDLT position. Moreover, *Parab et al*(5) and *Chou et al*(12) report the sensitivity of lung ultrasonography to confirm lung collapse at 88-100%. As a result, we hypothesized that lung ultrasonography is not inferior to fiberoptic bronchoscopy (non-inferiority study). Non-inferiority margin equal 10% with significant *p*-value as 0.05, power 90%, the sample size each group equal 82 cases. Furthermore, concerning drop out about 15%, sample size of each group was 100. Sample size calculation was demonstrated from n4Studies as

$$n_2 = \frac{(z_{1-\alpha} + z_{1-\beta})^2}{(\epsilon - \delta)^2} \left[\frac{p_1(1-p_1)}{k} + p_2(1-p_2) \right]$$
$$\epsilon = p_1 - p_2, \quad k = \frac{n_1}{n_2}, \quad n_1 = kn_2$$

For a non-inferiority or superiority trial for binary data

Proportion in group1 (p1) = 0.950

Proportion in group2 (p2) = 0.950

Non-inferiority or superiority margin (δ) = 0.100

Ratio between 2 groups (k) = 1.0

[figure not shown]
Alpha (α) = 0.05, Z (0.950) = 1.644854

Beta (β) = 0.10, Z (0.900) = 1.281552

Sample size: n1 = 82, n2 = 82

Statistical analysis was performed using SPSS version 18 for Windows (Chicago, USA). Continuous data were presented as the means and SD and statistical significance was considered when $p < 0.05$. The positive predictive value was calculated to determine the effectiveness of lung ultrasound compared to fiberoptic bronchoscopy and defined as follow: Positive predictive value (%) = TP/(TP+FP) x100

Figure 1: Trial profile

References

4. Cohen E. Double-lumen tube position should be confirmed by fiberoptic bronchoscopy. *Curr Opin Anaesthesiol.* 2004;17(1):1-6.
6. Lohser J. Evidence-based management of one-lung ventilation. *Anesthesiol Clin.* 2008;26(2):241-72, v.

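### Non-inferiority on surgeon-graded lung collapse cannot support the stated claim that ultrasound is comparable to bronchoscopy for confirming double-lumen tube position

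*Protocol*

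**What the plan says.** **The claim.** The protocol title says the study "compares lung ultrasonography to fiberoptic bronchoscopy confirming double lumen tube positioning for thoracic surgery". The Objectives section sets out to show that "using lung ultrasonography to confirm lung collapse resulted from proper positioning of the double lumen tube (DLT) is a comparable method", and it names the comparator as bronchoscopy: ultrasound "is a comparable method to using fiberoptic bronchoscopy to confirm the DLT position".

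**The two arms.** Under Interventions, the FOB arm has the tube position checked by bronchoscope and adjusted. In the US arm, "lung ultrasound was scanned in 4 zones including upper and lower lobe at flank and back of patient at the side of surgery", and the scan also guides repositioning if needed. No other scan field and no bronchoscopic check is described for that arm.

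**The outcomes.** Under Outcome Measurements: "The degree of lung collapse was determined by visual grading by surgeon". The other item is the time used to adjust the tube. The SAP's Statistical Analysis section compares the rate of lung collapse and duration, and adds a positive predictive value.

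**The protocol's own caution.** The Background calls bronchoscopy the gold standard for position and then states: "Though, proper tube positioning is not equal lung collapse". It also remarks that, in an earlier comparison of ultrasound with clinical methods, misplacement could not be ensured in either group.

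**The concern.** The claim concerns where the tube lies; the measurement concerns whether a lung collapsed. The Objectives and Interventions join the two by describing collapse as the result of proper positioning, a link that the Background declines to make.

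In the FOB arm, position is seen and corrected. In the US arm, the described scan looks at the side of surgery, and the outcome is again lung collapse. A tube that is misplaced but still allows good collapse would not lower the US arm's result. This blind spot matters in a non-inferiority trial because it can only flatter the new method: an excess of such tubes in the US arm leaves the endpoint unchanged. A reader of the title and objective would take a successful result to mean that ultrasound can stand in for bronchoscopy in confirming position, and the collapse data cannot show that.

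**Working it through.** **1. Reproduce the plan's figure.** Inputs from the protocol's Statistical Analysis section: p1 = p2 = 0.95, margin 0.10, one-sided alpha 0.05 (z = 1.644854), power 90% (z = 1.281552), ratio 1.

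n = (1.644854 + 1.281552)² × (0.0475 + 0.0475) / 0.10² = 8.5639 × 0.095 / 0.01 = 81.4, so 82 per group.

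This matches the plan. Allowing for 15% dropout, 82 / 0.85 = 96.5, so 97, which is consistent with the stated 100. The arithmetic is not at issue.

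**2. What the inputs measure.** The same section supports the bronchoscopy rate with a 95% sensitivity for optimal tube position, and the ultrasound rate with sensitivities of 88-100% for lung collapse. Both enter the formula as 0.95, so the two constructs are already mixed in the sample size.

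**3. What each endpoint can see.** In each arm, let
- a = share malpositioned with good collapse,
- b = share malpositioned with poor collapse,
- d = share well positioned with poor collapse.

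Correct position is 1 − a − b and good collapse is 1 − b − d. The differences, FOB minus US, are:
- position: (a_US − a_FOB) + (b_US − b_FOB)
- collapse: (b_US − b_FOB) + (d_US − d_FOB)

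The term in a is absent from the collapse difference. Write m = a_US − a_FOB for the excess.

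**4. Illustration.** Assumptions, none of them from the documents: 95% collapse success in both arms, 95% correct position with FOB, and b and d equal between arms. The collapse difference is then 0 and the position difference is m. Group sizes are those given under Interventions, 98 (FOB) and 97 (US). With the decision rule implied by the sample-size formula:

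chance of declaring non-inferiority = Φ[(0.10 − difference)/SE − 1.645], with SE = √(p_FOB(1 − p_FOB)/98 + p_US(1 − p_US)/97).

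- Collapse, any m: SE = √(0.0475/98 + 0.0475/97) = 0.0312; 0.10/0.0312 − 1.645 = 1.56; chance 94%.
- Position, m = 5 points (US 0.90): SE = √(0.0475/98 + 0.09/97) = 0.0376; 0.05/0.0376 − 1.645 = −0.31; chance 38%.
- Position, m = 10 points (US 0.85): the numerator is 0, so Φ(−1.645) = 5%.

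| Excess m | Non-inferior on collapse | Non-inferior on position |
|---|---|---|
| 0 | 94% | 94% |
| 2 points | 94% | 76% |
| 5 points | 94% | 38% |
| 10 points | 94% | 5% |

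**5. Does the predictive value close the gap?** The protocol defines it as TP/(TP + FP), but neither document's available text says which reference standard makes a positive true or false. It therefore cannot be taken as a check of position.

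**The case against.** The strongest reply is that this is a pragmatic comparison of two placement strategies on a shared functional outcome. Collapse is what the surgeon needs, and the Background's remark that position and collapse differ can be read as the reason for choosing collapse. The objective's wording is also a hybrid: it asks ultrasound to confirm collapse, not position. This stands as a defence of collapse as an endpoint. It does not defend the title, or an objective that declares comparability with a method whose task is to confirm position.

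Second, the text is incomplete. Part of the SAP was not available, so a position check described there cannot be excluded. This also stands, and the point is limited to the available text.

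Third, the illustration partly restates its premise: m is by definition invisible to the collapse endpoint. That is fair. The table shows what the blind spot could hide, not what happened.

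Stronger readings are tempting and are not supported:
- *That any malposition share above 10% in the US arm breaches the margin.* What matters is the difference between arms. If, as an assumption, 5% of FOB tubes and 12% of US tubes were malpositioned with good collapse, the excess would be 12 − 5 = 7 points, inside the margin if the other terms are equal.
- *That scanning was confined to the surgical side.* One field is described; no statement excludes others.
- *That a malpositioned tube was scored as a success.* No collapse grade is defined as success.
- *That the trial simply repeats the weakness noted in the earlier study.* Here, position in the FOB arm is confirmed and adjusted.

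**Conclusion.** The concern holds for the claim, not for the collapse comparison. On the available text, the trial can support a statement about surgeon-graded collapse. It cannot support one about confirming tube position, because position is not an outcome and the protocol itself separates the two. The randomised contrast on collapse and the sample-size arithmetic are untouched.

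Its size cannot be estimated from the documents, which give no value for the excess. On the assumed rates, a collapse analysis would pass about 94% of the time even if ultrasound were a full 10-point margin worse on position, where a position analysis would pass 5% of the time. A reader might infer that ultrasound missed malpositions in this trial, or that patients were put at risk. Nothing in the documents shows either.

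**What to change.** 1. Restate the objective and the permitted conclusion as: *ultrasound-guided DLT placement is non-inferior to FOB-guided placement for surgeon-graded collapse of the operative lung*. Bring the title into line.
2. In the Objectives and Interventions, remove the words that attribute collapse to proper positioning, and remove any claim of comparability for confirming tube position.
3. If later repositioning, unplanned bronchoscopy or ventilated-side events were already recorded, tabulate them by arm, descriptively. The documents do not say whether they were; if not, items 1 and 2 stand alone.

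Splitting the collapse result by left- and right-sided surgery is not a remedy: each half would still measure only collapse and would stay blind to malposition on the ventilated side.

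The cost is a change of wording and perhaps one table. The downside is a narrower claim. The protocol already reports enrolment and group sizes in the past tense, so a position endpoint could not readily be added now, and narrowing the claim is the practical course.

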## Statistical Analysis

Sample size calculation was performed by n4Studies with the hypothesis that lung ultrasonography is not inferior to fiberoptic bronchoscopy (non-inferiority study) 10, 18, 19. Non-inferiority margin equal 10% with significant *p*-value as 0.05, power 90%, the sample size each group equal 82 cases. Furthermore, concerning drop out about 15%, sample size of each group was 100.

Statistical analysis was performed using SPSS version 18 for Windows (Chicago, IL). Continuous variables with normal distribution were presented as means and standard deviation, non-normal variables were report as median and interquartile range. Comparison of demographic data, rate of lung collapse and duration were made with the independent t test, Mann Whitney U test or Pearson's chi-squared test. Statistical significance was represented by *p* value <0.05. The positive predictive value was calculated to determine the effectiveness of lung ultrasound compared to fiberoptic bronchoscopy.

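### Effectiveness is judged by positive predictive value, which conditions on a post-randomisation test result and omits test-negative patients; the all-patient collapse rate should be the named measure, tested against the 10-point margin

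*Protocol*

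**What the plan says.** The Protocol sets out its design as follows: "Design: a non-inferiority randomized controlled study". In both arms the test is used to correct the tube as well as to check it. Bronchoscopy confirms the position and the tube is adjusted; ultrasound is used "to confirm the lung collapse resulted from proper positioning of the DLT and used to aid repositioning of the DLT if required". The outcome is the surgeon's visual grade of lung collapse.

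For effectiveness, the Protocol's Statistical Analysis section states "The positive predictive value was calculated to determine the effectiveness of lung ultrasound compared to fiberoptic bronchoscopy and defined as follow", followed by "Positive predictive value (%) = TP/(TP+FP) x100". The SAP's Statistical Analysis section says the same without the formula: "The positive predictive value was calculated to determine the effectiveness of lung ultrasound compared to fiberoptic bronchoscopy".

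The SAP has one other relevant sentence: "Comparison of demographic data, rate of lung collapse and duration were made with the independent t test, Mann Whitney U test or Pearson's chi-squared test". It does not call the collapse rate the effectiveness measure and does not refer it to the margin. The 10-point margin appears in both documents only in the sample-size text.

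**The concern.** PPV answers a diagnostic question: among patients whose test was positive, how many truly had the condition? The trial asks which strategy more reliably ends with a collapsed lung. Three things separate the two.

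- **The denominator is not the randomised group.** TP+FP holds only test-positive patients. Someone whose scan never showed collapse, and whose lung the surgeon found not collapsed, is a failure of the strategy but is absent from PPV. A collapsed lung that the test missed is absent too.
- **A positive test differs by arm.** On ultrasound it is collapse seen; on bronchoscopy it is the tube seen in position. The Protocol's Background itself notes that a well-placed tube does not guarantee collapse. The two PPVs thus condition on different events.
- **The planning assumption is a different quantity.** The 95% in the sample-size calculation is taken from a reported sensitivity and applied to whole groups of 82.

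At stake is whether the measure used to judge effectiveness preserves the randomised comparison.

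**Working it through.** **Inputs from the Protocol.** p1 = p2 = 0.95; margin 0.10; z = 1.644854 (alpha 0.05, hence one-sided) and 1.281552 (90% power); equal allocation; groups of 98 (bronchoscopy) and 97 (ultrasound) after five of 200 were dropped.

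**Step 1: the plan's own figure.** n = (1.644854 + 1.281552)² × (0.95×0.05 + 0.95×0.05) / 0.10² = 8.5639 × 0.095 / 0.01 = 81.36, rounded up to 82. This matches. It also fixes the scale for what follows: a one-sided 5% comparison of proportions over all patients in each group.

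**Step 2: what each measure counts.** In an arm of N patients:

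- PPV = TP / (TP + FP)
- all-patient collapse = (TP + FN) / N, with N = TP + FP + TN + FN if every test is readable

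The two are equal when TN = FN = 0, that is, when every tube ended test-positive. Otherwise they can differ.

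**Step 3: illustration.** The documents give no count of test-negatives, so these are assumptions: bronchoscopy 93/98 collapsed (94.9%) with no test-negatives; ultrasound with 4 false positives and k test-negatives, so TP = 97 - 4 - k. The lower limit is d - 1.645 × √[pU(1-pU)/nU + pB(1-pB)/nB], where d = pU - pB, U is ultrasound and B is bronchoscopy.

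For k = 5, TP = 88:

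- PPV: 88/92 = 95.65%; d = +0.75 points; standard error 3.08; lower limit -4.3.
- All patients, none of the five collapsed: 88/97 = 90.72%; d = -4.18 points; standard error 3.69; lower limit -10.2.

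| Ultrasound test-negatives (k) | PPV | PPV lower limit | All-patient collapse, none of k collapsed | Lower limit | Lower limit if half of k collapsed |
|---|---|---|---|---|---|
| 0 | 93/97 = 95.9% | -4.0 | 93/97 = 95.9% | -4.0 | -4.0 |
| 4 | 89/93 = 95.7% | -4.2 | 89/97 = 91.8% | -9.0 | -6.5 |
| 5 | 88/92 = 95.7% | -4.3 | 88/97 = 90.7% | -10.2 | (odd) |
| 6 | 87/91 = 95.6% | -4.4 | 87/97 = 89.7% | -11.5 | -7.8 |
| 8 | 85/89 = 95.5% | -4.5 | 85/97 = 87.6% | -13.9 | -9.0 |
| 10 | 83/87 = 95.4% | -4.7 | 83/97 = 85.6% | -16.2 | -10.2 |

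If all k had collapsed lungs, the all-patient figure is 93/97 and the limit is -4.0 whatever k is.

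**Step 4: does the SAP's collapse-rate test fill the gap?** Take k = 8 with none collapsed: 85/97 against 93/98. The pooled rate is 178/195 = 0.913, z = 0.0727 / √[0.913×0.087×(1/97 + 1/98)] = 1.80, and the chi-squared p value is 0.07. A difference test at 0.05 is not significant although the lower limit is -13.9. The comparison would be reported, but this test does not address the margin.

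**Step 5: the other direction.** Put the test-negatives in the bronchoscopy arm instead: ultrasound 93/97 with none; bronchoscopy with 5 test-negatives not collapsed, 5 false positives and 88 true positives. On PPV the difference is 93/97 - 88/93 = 95.9% - 94.6% = +1.3 points. On all patients it is 93/97 - 88/98 = 95.9% - 89.8% = +6.1 points. Here PPV understates ultrasound.

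**The case against.** The strongest reply is that the all-patient comparison is already planned. The surgeon's grade is the outcome for both groups, the SAP compares the collapse rate, and nothing restricts that rate to test-positives. This stands in part: test-negative patients leave the PPV, but not necessarily every analysis. It is not a cure, because that comparison is neither called the effectiveness measure nor tied to the margin, and no rule says which result prevails if the two disagree.

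A second reply is that repositioning may have continued until the test was positive, so that PPV equals the collapse rate. The Protocol says ultrasound was "used to aid repositioning of the DLT if required", which neither requires nor excludes this. Parts of the SAP ahead of its Statistical Analysis section were not available to me and may define true and false positives, so I do not count the lack of a definition as a fault. The point needs only the formula: a test-negative patient is in neither TP nor FP.

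A reader might go further and infer that the plan would declare ultrasound non-inferior on PPV, or that the bias favours ultrasound. The documents support neither. No sentence tests a PPV difference against the 10-point margin. The direction depends on which arm has more test-negatives or failed tests and on how those lungs fared; the Protocol's Background says that bronchoscopy, too, can be hard or unachievable in some patients.

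**Conclusion.** The point holds as a matter of definition. Both documents judge effectiveness by a quantity whose denominator is set after randomisation, by a test whose positive result differs between arms, and which leaves out test-negative patients, including any whose lung did not collapse.

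The size in this trial cannot be known from the documents. The divergence from 5 of 97 test-negatives is the extreme case: no bronchoscopy test-negatives and no collapsed lungs among the ultrasound test-negatives. Under milder splits, 8 of 97 stays inside the margin. The figures show that PPV and the all-patient rate can disagree about the margin, not that they did.

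I grade this as something that should be fixed rather than a fatal flaw, because the harm depends on an unknown and possibly zero number of test-negatives, and the outcome data needed are already part of the plan.

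**What to change.** In the Statistical Analysis sections of both documents, replace the PPV sentence with wording to this effect:

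*Effectiveness is the proportion of all patients in each randomised group with successful lung collapse on the surgeon's visual grade, whatever the final result of the assigned test. Patients whose test stayed negative or could not be read remain in the denominator. Non-inferiority is assessed by comparing the one-sided 95% lower confidence limit of the difference (ultrasound minus bronchoscopy) with -10 percentage points.*

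Keep PPV as a descriptive secondary measure within each arm, reported with the number of patients outside its denominator.

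The cost is a wording change; the surgeon's grade is already the outcome, so no new data are needed. The downside is that the success rate in either arm may look slightly less favourable than its PPV.
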